## **XII. DATA ANALYSIS AND MANAGEMENT**

Data management and analysis will be led by the University of Alabama at Birmingham under the supervision of the study PI ([name]).

The primary analysis will be by intention to treat for women who are randomized and receive at least 1 dose of study medication.

The “per protocol” analysis will be performed on women who came to at least one follow up visit following the enrollment visit, reported excellent (>90%) medication adherence, and had outcomes captured (ie – not lost to follow up).

**Statistical Analysis:** Descriptive statistics will be used to compare the study participants between each arm and the primary analysis will be intention-to-treat for the primary outcome of proportion of women with parasitemia. The analysis plan for categorical outcomes is chi-square, Fisher’s exact tests as needed for small sample sizes and we plan to use t-test and Wilcoxon Rank-Sum tests for continuous outcomes. Women will be considered lost to follow up if they do not have a study visit after 35 weeks or at delivery for outcome ascertainment.

For the secondary outcomes, the significance of differences in proportion will be explored using the Pearson’s  $\chi^2$  test or Fisher’s exact test. Multivariable regression modeling will be used to evaluate baseline factors associated with parasitemia if there is imbalance between the arms despite randomization. Potential covariates include age, parity, educational level, monthly income, marital status, history of negative birth outcomes, CD4 count, ART adherence, bed net usage, malaria treatment received and number of study visits. All analyses will be performed in SAS v 9.3.

**Data Management:** Data will be collected in clinic on paper forms to be entered into a password-protected, secure, web-based, electronic database (REDCap). Information will be stored locally on the device, then transferred to a server located at the University of Alabama at Birmingham when the internet access is adequate. On site, the paper forms will be kept in a locked cabinet in a room with the study staff and the computer for data entry will be password protected. During the conduct of the study, periodic data checks will occur to systematically evaluate for any missing data or unanticipated problems. The site staff will receive feedback to improve the process as indicated. Adverse events will be reviewed weekly by the PI who will be blinded to study arm randomization. The final data analysis will occur after all participants have been enrolled and procedures completed at both sites.

REDCap (Research Electronic Data Capture) is a secure, Web-based application designed to support data capture for research studies. For multi-center studies, Data Access Groups may be set up to allow users access only to their site’s data. For quality control purposes, REDCap offers real-time range checking during data entry. There are also data visualization tools to assist in data cleaning and evaluation. The Data Export Tool includes methods for data de-identification and exports some or all data to Excel, SAS, SPSS, R, S-Plus, and Stata.

The REDCap database is hosted at the UAB Department of Medicine’s secure data center, which will be used as a central location for data storage, processing, and management. The servers are protected by an aggressive firewall and a log monitoring system. All web communications are protected via SSL encryption. Only IRB approved research team members will have access to the REDCap. Access is granted according to “the principle of least privilege.” Each team member will be granted access to the REDCap data system through a secure login.

The protocol has been registered on clinicaltrials.gov with the study ID number NCT03431168.

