#### a) Primary Outcomes

**Aim 1** Proportion of women with *Plasmodium falciparum* peripheral parasitemia by microscopy or PCR.

**Aim 2** Prevalence of a composite STI measure (GC, CT, syphilis infections) will be measured in both groups in late pregnancy (>35 weeks gestation) or at delivery and compared between the two groups.

[figure not shown]
**Aim 3** a) Mean infant birthweight; b) Proportion with adverse birth outcomes, including low infant birthweight (<2500 gm), miscarriage (<28 weeks), preterm delivery (<37 weeks), small for gestational age (SGA), stillbirth (>28 weeks), congenital anomaly at birth, early neonatal mortality (within 7 days); and c) maternal adherence to and tolerance of the prophylactic regimen (vomiting, rash/allergic reactions, dizziness, weakness).

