## **XI. SAMPLE SIZE CONSIDERATIONS**

AIM 1: To test the hypothesis that the addition of AZ to standard preventive therapy in pregnant women with HIV will be associated with a lower proportion of women with peripheral parasitemia detected by microscopy or PCR at delivery, we assumed a 30% prevalence of parasitemia in the TMPS arm based on prior studies and 15% prevalence in the TMPS/AZ arm. A sample size of 134 pregnant women per arm has 80% power at a two-sided significance level of 0.05 using a chi-square.

We will plan for 15% loss to follow up (LFU) and will recruit 154 women per arm (308 women total).

AIM 2: Based on the sample size of 308 evaluable participants at the time of delivery and an expected prevalence of 30% for one or more STIs (CT 20%, GC 5%, syphilis 5%) there will be >80% power at a two-sided significance level of 0.05 to detect a 50% lower STI prevalence in the intervention arm.

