## Appendix A – DESIGN SUMMARY

The PREMISE Trial: A Randomized Clinical Trial to Prevent Malaria and STI in Pregnant Women with HIV			
OBJECTIVE To determine whether or not the addition of Azithromycin (AZ) to standard Cotrimoxazole prophylaxis reduces infection in Cameroon			
ORGANIZATION	SCHEDULED EVALUATIONS/DATA COLLECTION		
Clinical Centers	Mboppi Hospital in Douala, Cameroon Baptist Hospital in Mutengene, Cameroon University of Alabama at Birmingham, US	Pre randomization:	# History, GA, HIV status
Principal Investigator	[name]	Post randomization:	# thick smear, DBS and vaginal swab # visits scheduled q 4 weeks to assess medication adherence and tolerance # sick call visits for fever or complications # thick smear, DBS and vaginal swab # placental collection
DESIGN	Near Term or Delivery:		
Type:	# Phase II, Double masked RCT	OUTCOME MEASURES	
Major Eligibility Criteria:	# HIV-infected # Age $\geq$ 16 # GA 4-28 weeks # Singleton pregnancy	Primary:	# proportion with peripheral parasitemia by PCR or microscopy # composite STI score (GC/CT/syphilis) # safety and mean infant birthweight
Groups:	# Experimental: AZ/Cotrimoxazole # Placebo: Cotrimoxazole	Secondary:	# episodes of symptomatic malaria # proportion with placental parasitemia # composite adverse birth outcomes # maternal anemia (hgb <11 g/dL) # anogenital GBS colonization # proportion with other STI (Mycoplasma genitalium, Trichomonas vaginalis, BV)
Random Allocation:	1:1 allocation	TIMETABLE	
Stratification:	By clinical site	As designed:	# Enrollment: January 2018-July 2019 # Data Collection: January 2018-Dec 2019 # Final Analysis: June 2020
Sample Size:	308 subjects		
Assumptions:			

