# Outcome event: peripheral parasitemia			
# Placebo group event rate: 30%			
# Experimental group event rate: 15%			
# 15% loss to follow up			
# Type 1 error 5% (2-sided)			
# Power 80%			

Registered at Clinical Trials Website ([clinicaltrials.gov](https://clinicaltrials.gov)): NCT03431168

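### Section III.a and Appendix A list primary outcomes for three aims, Section XII names one, and no testing order is set: false-positive risk is up to about 10% if Aims 1 and 2 both count as primary

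*Combined protocol and SAP*

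**What the plan says.** The current sections give different answers to the question of what is primary.

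- **Section XII** has one primary outcome: the intention-to-treat analysis is for "the primary outcome of proportion of women with parasitemia".
- **Appendix A, assumptions**, names peripheral parasitemia as the outcome event and puts "Type 1 error 5% (2-sided") under it.
- **Section III.a** lists five outcomes under its primary heading. They are parasitemia (Aim 1), "Prevalence of a composite STI measure (GC, CT, syphilis infections") (Aim 2), and three lettered Aim 3 items: "Mean infant birthweight", adverse birth outcomes, and maternal adherence and tolerance.
- **Appendix A, outcome measures**, has three primary entries: parasitemia, "composite STI score (GC/CT/syphilis"), and safety with mean birthweight. It puts composite adverse birth outcomes among the secondaries. Section III.b also lists adverse birth outcomes as secondary, under Aim 1.
- **Section I.b** states one primary hypothesis covering malaria, syphilis, CT, GC and GBS together. GBS is only a secondary outcome in Section III.b.
- **Section XI** sizes Aim 1 with "A sample size of 134 pregnant women per arm has 80% power at a two-sided significance level of 0.05 using a chi-square". For Aim 2 it claims more than "80% power at a two-sided significance level of 0.05 to detect a 50% lower STI prevalence in the intervention arm". It gives neither an alpha nor a power calculation for Aim 3.

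No section gives a testing order, an alpha split or a rule for calling the trial positive.

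**The concern.** The plan should fix, before unblinding, which result answers the primary hypothesis. Here it does not. Suppose parasitemia shows no difference and the STI composite is significant. By Section XII the primary analysis has failed. By Section III.a and Appendix A a primary outcome has succeeded. Both readings could be defended from the protocol, and the choice could be made after the data are seen.

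The 5% type 1 error in Appendix A describes parasitemia taken alone. It does not describe a trial in which Aims 1 and 2 each have the full 0.05 and either may be presented as the primary finding. Section XII marks only the secondary outcomes as exploratory, so it does not settle the status of the Aim 2 and Aim 3 outcomes that Section III.a calls primary.

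**Working it through.** **Inputs.** Section XI: "we assumed a 30% prevalence of parasitemia in the TMPS arm based on prior studies and 15% prevalence in the TMPS/AZ arm"; two-sided 0.05; 80% power; 308 recruited with 15% loss. For Aim 2, Section XI expects 30% prevalence and a 50% reduction, so also 30% v 15%. Appendix A: 1:1 allocation.

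**1. Reproduce 134 per arm.** The mean proportion is 0.225 and the difference is 0.15.

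- Uncorrected: n = [1.960 × √(2 × 0.225 × 0.775) + 0.8416 × √(0.30 × 0.70 + 0.15 × 0.85)]² / 0.15² = (1.1575 + 0.4889)² / 0.0225 = 120.5, so 121.
- Continuity-corrected: n′ = (n/4) × [1 + √(1 + 4/(n × 0.15))]² = 30.12 × 2.105² = 133.5, so **134**.

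The stated figure is matched with the full two-sided 0.05 spent on Aim 1. Nothing was held back for Aim 2.

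**2. False-positive chance if any one of k outcomes may be claimed.** With independent tests at 0.05 and all nulls true, it is 1 − 0.95^k.

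| Outcomes counted | k | Chance | Basis for 0.05 |
|---|---|---|---|
| Parasitemia only | 1 | 5.0% | Stated |
| Aims 1 and 2 | 2 | 9.75% | Stated for both |
| Appendix A's three entries | 3 | 14.3% | Assumed for the third |
| All five in III.a | 5 | 22.6% | Assumed for the three Aim 3 items |

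Only the first two rows rest on documented significance levels. The last row counts each lettered Aim 3 item as one test.

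**3. Sensitivity to correlation.** The documents give no correlations, so these are assumed. Simulating equally correlated normal test statistics gives:

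| Correlation | k = 2 | k = 5 |
|---|---|---|
| 0.3 | 9.5% | 20.8% |
| 0.5 | 9.1% | 18.3% |
| 0.8 | 7.8% | 12.7% |

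Counting only errors in one direction (0.025 per test), independence gives 1 − 0.975² = 4.9% for two outcomes and 1 − 0.975⁵ = 11.9% for five.

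**4. Power under a testing order.** Evaluable women: 308 × 0.85 = 261.8, about 131 per arm. Section XIII gives 268, which is 134 per arm. Section XI treats all 308 as evaluable for Aim 2, which is 154 per arm. Uncorrected chi-square power at 131 per arm is Φ[(0.15 × √131 − 1.960 × 0.5906) / 0.5809] = Φ(0.963) = 83.2%. Because the assumed rates are the same, this applies to each aim.

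If the STI test counts as confirmatory only after a significant parasitemia result, and the tests are independent with both effects as planned, the chance that Aim 2 is confirmatory is the product of the two powers:

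| Evaluable per arm | Each aim alone | Aim 2 after Aim 1 |
|---|---|---|
| 131 | 83.2% | 0.832² = 69% |
| 134 | 84.0% | 0.840² = 71% |
| 154 | 88.7% | 0.887² = 79% |

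If azithromycin has no effect on parasitemia but the planned effect on STIs, that chance at 131 per arm is 0.05 × 0.832 = 4.2%.

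For comparison, splitting alpha to 0.025 each lowers Aim 1 power from 83.2% to 75.1% at 131 per arm. By the continuity-corrected formula, the 80% power requirement would then be 160 per arm, not 134.

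**The case against.** The strongest reply is that the primary test is already settled. Section XII, the sample size and the Appendix A assumptions all point to parasitemia, and on that reading the error rate is 5%. The trial is also a Phase II test of concept with separate aims, where testing each aim without adjustment is a defensible choice.

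Much of this stands. No passage says that one significant outcome makes the trial positive, and a Phase II trial need not adjust every outcome. But that does not remove the conflict: Section III.a and Appendix A are current text, and they label other outcomes primary without qualification.

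A reader might go further and infer that all three aims are tested at 0.05, so that the false-positive chance simply is 10% to 23%. The documents do not support that, for three reasons.

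- The 0.05 level is stated for Aims 1 and 2 only.
- Section I.c frames Aim 3 as collecting safety, adherence and tolerability data. A difference in vomiting or rash would not be presented as proof of efficacy.
- Independence fails within Aim 3: mean birthweight and birthweight below 2500 g come from the same infants, which pulls the five-outcome figure down.

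**Conclusion.** The inconsistency is real and should be removed. Sections III.a and XII and Appendix A disagree on the number of primary outcomes, and Section XI gives the full 0.05 to two aims with no order between them.

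The size that the documents support is a false-positive chance of up to about 10%, roughly double the stated 5%. It rests on three conditions: a significant result on either Aim 1 or Aim 2 would be reported as a positive primary result, the two tests are independent, and both nulls are true. The figure near 23% is only a conditional upper bound for the five listed outcomes and should not be quoted as the trial's error rate. If Section XII alone governs, the rate is 5%.

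**What to change.** 1. Change Section III.a and Appendix A to agree with Section XII: parasitemia is the single primary outcome, tested at two-sided 0.05.
2. State in Section I.b that parasitemia decides the primary hypothesis.
3. Make the STI composite the key secondary outcome, tested at two-sided 0.05 and called confirmatory only if parasitemia is significant. Otherwise report it as supportive.
4. Report all Aim 3 outcomes, including birthweight, as safety and tolerability estimates with 95% CIs and no confirmatory claim. Make the status of adverse birth outcomes the same in Sections III.a and III.b and Appendix A.

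**Cost.** Aim 1 keeps its alpha, power and sample size. The cost falls on Aim 2, whose chance of a confirmatory result drops from about 83% to about 69% under the assumptions in step 4 of the working, and much further if azithromycin does not reduce parasitemia. An alpha split would protect Aim 2 from that, but at the price to Aim 1 shown there. The change needs a protocol amendment, which Section XIV requires to go to both IRBs, and it should be in place before unblinding.

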##### b) Participant Inclusion Criteria

- Confirmed HIV-infection (documented in medical record)
- Age  $\geq 16$  years
- Confirmed pregnancy,  $<28$  weeks estimated gestational age (by best obstetric estimate which may include ultrasound or fundal height and LMP)
- Live singleton pregnancy

- Receiving prenatal care at Mboppi Hospital or Mutengene Hospital
- Plan to receive follow up prenatal care and deliver at study facility
- Capable of providing written informed consent
- Able and agree to come to facility for febrile episodes or acute illness during pregnancy (with reimbursement of transportation costs).
- Agree to avoid antimalarial medications outside of study protocol.
- Women receiving standard therapy for HIV infection (any antiretroviral regimen) and standard malaria prophylaxis medications (cotrimoxazole) will be eligible to participate.
- Women with HIV-infection who are not taking antiretrovirals (for any reason) are eligible to participate in the trial if all other study criteria are met.
- Participants will be eligible to participate irrespective of prior or active malaria infection detected at the time of study enrollment.

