### **d) Randomization Method and Masking**

Consenting women will be assigned to one of two prophylaxis groups with a computer generated variable size (2, 4, 6) block randomization sequence prepared in advance by a co-investigator at the University of Alabama at Birmingham. The active and placebo study medication will be indistinguishable in appearance and packaged according to the randomization sequence so that the patient is randomized when she is assigned to the next available individual supply of study medication. The study is double masked; neither the patient nor the clinical staff will be aware of the assigned prophylaxis.

Randomization will be stratified by clinical center to assure balance between the two study groups with respect to anticipated differences among the clinic populations and possible differences in patient management. A unique study ID will be provided to each patient after they are randomized (starting with 5001D for the Douala site, starting at 9001M for the Mutengene site).

The PI and all staff responsible for assessing outcomes (laboratory and clinical) will be blinded to the randomization arm.

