## VII. STUDY SCHEDULES AND PROCEDURES

	Screen and Enroll	Follow up Visit (1-6)	Sick Visit (1-9)	Term Visit (1)	Delivery Visit (1)	Postpartum (if no Delivery Visit)	Follow Up Call	Infant Follow Up Call or Visit
Timing of Visit/Call	4-28 weeks	Every 4 weeks	As Needed	35-42 weeks	At Delivery	Within 14 days of delivery 	Within 6 weeks	3, 6, 9, 12 months
FORMS 								
Screening Log (Form 1)	X							
Eligibility (Form 2)	X							
Consent and Randomize (Form 3,4)	X							
Baseline Survey (Form 5)	X							
Follow Up Survey (Form 6)		X		X	X	X		
Med Adherence (Form 7)		X	X	X	X	X		
Sick Call Survey (Form 8)			X					
Outcomes and Labs (Form 9)	X	X	X	X	X	X	X	
Adverse Events (Form 10)		X	X	X	X	X	X	X
Postpartum Phone Call (F 11)							X	
Participant Contact Info (Form 12)	X	X	X	X	X	X	X	
Infant Follow Up (Form 13)								X
CLINICAL AND SAMPLING								
Vitals and Exam	X	X	X	X	X	X		
Venipuncture	X		X	X	X	X		
Finger stick	X	X	X	X	X	X		
Vaginal Swab	X			X	X	X		
Placental biopsy					X			
Directly Observed Therapy	X	X	X	X				
LAB TESTING 								
CBC and differential	X			X	X	X		
CD4 Count				X				
HIV Viral Load					X			
Thick smear	X			X	X	X		
RDT		X	X	X				
DBS for PCR	X	X	X	X	X	X		
Syphilis (RPR/TPHA)	X 			X	X	X		
Xpert GC/CT & GBS NAAT				X	X	X		
SUPPLIES PROVIDED								

Bed Net	X							
Condoms	X	X	X	X				
30 day med supply	X	X	X	X				

 Samples collected at postpartum visit only if they were not collected at prior visits

 Lab testing to be performed on site. Additional testing at UAB is not part of this table.

 In cases of fever or clinical suspicion of malaria.

 RPR testing will be performed for women with a positive treponemal test on enrollment if it has not been done.

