### a) Enrollment Visit

Following the provision of informed consent, study subjects will be randomized to one of two arms. A baseline survey will be administered by study nurses, vital signs will be collected and a brief exam will be performed. The medical chart will be reviewed for additional information. A 30 day supply of medications will be provided by study nurse. Contact information will be collected for the woman and a back-up person (with permission) and women will be given an appointment to return in 30 days. Bed nets, condoms and safe sex counseling will be provided. Partner HIV testing will be recommended, discussed with all women and facilitated, as necessary. Questions will be asked by study staff and entered into a RedCAP database. All forms will be labeled with the unique study ID, visit number and date.

Testing: CBC, thick smear and DBS. RPR confirmatory testing for those with + ANC syphilis screen. Vaginal swab for GC/CT and store. pH. Slides and store.

Treatment: For malaria peripheral parasitemia:

1st trimester – Quinine.

National Guidelines: Three doses of Parenteral Quinine base at 8.3mg/kg x 3 every 8 hours for 24 hours. Each infusion should run for 4 hours. This is relayed by Oral Quinine (tablets) for 3 days if patient can tolerate) and a maximum dose of 1.5 per day of Quinine base. The treatment is for 7 days. If the woman develops contractions on quinine, administer tocolytics.

2nd or 3rd trimester - Artesunate.

Per National Guidelines: Injectable Artesunate IV or IM: 2.4mg/kg at 0, 12, and 24 hours. This is continuous once every 24 hours until the patient can take the oral with ease. This is relayed with Artemether -Lumefantrine for 3 days if she can swallow.

1st dose of study medications will be given under directly observed therapy (DOT).

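### The Aim 1 chi-square is valid but uses neither the site stratum nor enrolment parasitemia, and the only regression has an undefined trigger and lists post-randomisation covariates as baseline factors

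*Combined protocol and SAP*

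**What the plan says.** **Primary test.** Section XII (Data Analysis and Management) says "The analysis plan for categorical outcomes is chi-square", with Fisher's exact test where samples are small. Section XI (Sample Size Considerations) sizes Aim 1 on a chi-square: 134 per arm, 30% versus 15%, two-sided 0.05, 80% power.

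**Site.** Section V.d (Randomization Method and Masking) says "Randomization will be stratified by clinical center to assure balance between the two study groups with respect to anticipated differences among the clinic populations". No section carries site into an analysis.

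**Enrolment parasitemia.** Section V.b (Participant Inclusion Criteria) says "Participants will be eligible to participate irrespective of prior or active malaria infection detected at the time of study enrollment". Section VII.a (Enrollment Visit) schedules "Testing: CBC, thick smear and DBS", and the schedule table in Section VII marks both malaria samples at enrolment. Enrolment status is in neither the primary test nor the named covariates.

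**Regression.** The only adjustment in Section XII is this: "Multivariable regression modeling will be used to evaluate baseline factors associated with parasitemia if there is imbalance between the arms despite randomization". No criterion for imbalance, model form, effect measure or selection rule follows. The list of 11 potential covariates ends with "CD4 count, ART adherence, bed net usage, malaria treatment received and number of study visits".

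**The concern.** A design that stratifies randomisation because it expects the sites to differ would normally analyse by that stratum. A baseline value of the outcome itself, already scheduled for every woman, is the natural second stratifier. Leaving both out gives up precision that costs little to keep.

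The regression raises a different problem. Number of study visits accrues after randomisation. Malaria treatment received does too on its natural reading: Section VII.a says "Following the provision of informed consent, study subjects will be randomized to one of two arms" before it lists testing and treatment, and Sections VII.b to VII.e provide treatment throughout follow-up. Azithromycin is being tested because it may reduce malaria, so it may also reduce malaria treatment. An effect estimate that conditions on a consequence of the drug can be biased, and a larger sample does not remove that. With no definition of imbalance, whether and how the model is run can be settled after the data are seen.

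**Working it through.** **1. The plan's sample size.** Inputs from Section XI: 0.30 versus 0.15, mean 0.225, two-sided 0.05, 80% power.

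n = [1.960 × √(2 × 0.225 × 0.775) + 0.842 × √(0.30 × 0.70 + 0.15 × 0.85)]² / 0.15² = 120.5, so 121 per arm.

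With continuity correction: n′ = (n/4) × [1 + √(1 + 4/(0.15n))]² = 133.5, so 134. The plan's figure reproduces only with the correction.

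**2. Power at the planned loss.** 154 × 0.85 = 130.9, so 131 per arm.

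- Uncorrected: z = (0.15 − 1.960 × √(0.34875/131)) / √(0.3375/131) = 0.963, power 83.2%.
- Corrected (subtract 1/131 from 0.15): z = 0.812, power 79.2%.
- At 134 per arm: 84.0% and 80.2%.

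So 3 women per arm are worth about 0.8 points (84.0 − 83.2).

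**3. Crude chi-square against CMH by site and enrolment status.** 60,000 simulated trials per scenario; 131 per arm; sites 87:44 per arm (from 12:6 monthly enrolment, Section XIII); overall 30% versus 15%; both tests uncorrected; complete status; enrolment positivity assumed 30%. Strata with fewer than 10 women were merged into the same site's negative stratum. Both odds ratios are assumptions.

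| Enrolment-status OR | Site OR | Crude power | CMH power | Change |
|---|---|---|---|---|
| 1 | 1 | 83.7 | 83.3 | −0.4 |
| 2 | 2 | 84.0 | 84.9 | +0.9 |
| 3 | 1.5 | 83.9 | 85.4 | +1.5 |
| 5 | 2 | 83.8 | 87.6 | +3.8 |
| 8 | 2 | 84.0 | 89.9 | +5.9 |

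- A run without merging gave 83.9 vs 83.5, 84.1 vs 84.8, 83.6 vs 85.0, 84.2 vs 87.9 and 84.1 vs 89.9 at enrolment-status OR 1, 2, 3, 5 and 8: the same pattern, with +0.7 at OR 2.
- Part of the gain is due to site. Stratifying by enrolment status alone at OR 2 (134 per arm) gave 84.8 vs 85.1. Stratifying by site alone gave 0.0, +0.1, +0.4 and +1.2 at site OR 1, 1.5, 2 and 3.
- At 10% positivity the five changes are −0.3, +0.4, +0.6, +1.8 and +2.9.
- At 30% positivity with status missing for 20%, they are −0.6, +0.3, +0.8, +2.7 and +4.5.
- Null rejection: crude 4.7–5.0%, CMH 4.8–5.1%. When the sites differ widely the crude test is conservative (4.5% at a 20-point site difference, 134 per arm).

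**4. Chance imbalance in enrolment parasitemia.** At 30% prevalence the SD of the arm difference is √(2 × 0.3 × 0.7/131) = 5.7 points, and P(10 points or more, either direction) = 7.7%. Take 5 points extra in one arm and 5 fewer in the other.

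- OR 2: outcome risk is 25.5% versus 40.6% by enrolment status in the 30% arm (gap 15.1) and 12.1% versus 21.7% in the 15% arm (gap 9.5). Shift = 0.05 × 15.1 + 0.05 × 9.5 = 1.2 points.
- OR 5: gaps are 35.2 and 22.7. Shift = 0.05 × 35.2 + 0.05 × 22.7 = 2.9 points.

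**5. Conditioning on malaria treatment.** Assume treatment in 30% versus 15%, outcome in 30% versus 15%, and an unmeasured exposure in half the women that raises the odds of both by k. Given exposure, treatment and outcome are independent. The true difference is −15.0.

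For k = 8, solving for the risks gives 10.8% unexposed and 49.2% exposed in the control arm, and 4.2% and 25.8% in the azithromycin arm, for treatment and outcome alike.

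- Untreated women: control 0.5 × (0.892 × 0.108 + 0.508 × 0.492)/0.70 = 24.7%; azithromycin 13.6%; difference −11.1; weight 0.70 × 0.85/1.55 = 0.384.
- Treated women: control 0.5 × (0.108² + 0.492²)/0.30 = 42.3%; azithromycin 22.8%; difference −19.5; weight 0.30 × 0.15/0.45 = 0.100.
- Mantel-Haenszel difference: (0.384 × −11.1 + 0.100 × −19.5)/0.484 = −12.8.

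For k = 2, 3 and 5 the result is −14.7, −14.3 and −13.6. A true zero (30% in both arms) becomes +0.4, +0.9, +1.7 and +2.6 for k = 2, 3, 5 and 8.

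**The case against.** The strongest reply is that the chi-square is prespecified, valid, and the test on which this Phase II test-of-concept was sized. Preferring CMH is then a matter of efficiency, and the efficiency is modest: at an enrolment-status odds ratio of 1 to 2 it is about nil. Section VII.a also schedules treatment of parasitemia found at enrolment, and the outcome is measured in late pregnancy or at delivery, which may put the gain at the low end. All of this stands. It limits the size of the point but gives no reason to leave the stratum out.

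On the regression, Section XII does not say that the model yields an adjusted treatment effect. The sentence sits in a paragraph that opens with the secondary outcomes, and the covariates are only potential and not exhaustive. This stands too, so the bias in step 5 is conditional on that use. It does not rescue a list of baseline factors that contains number of study visits. Treatment given at enrolment before the first dose could fairly count as baseline, so the objection to malaria treatment received applies to treatment after enrolment.

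Three stronger readings are tempting but unsupported:

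- **That CD4 count, ART adherence and bed net usage are also post-randomisation.** The schedule table as extracted marks CD4 only at the term visit and the adherence form only from follow-up, but the table is damaged. Section VII.a includes a baseline survey and chart review whose contents are not shown, so enrolment values may exist.
- **That the regression may displace the chi-square as the primary result.** Nothing in Section XII says so.
- **That a 10-point imbalance shifts the estimate by 1.5 to 3.5 points.** Those figures apply the 30% control risk to both arms. With the planned 30% and 15% the shift is 1.2 to 2.9, and the 5% error rate already allows for chance imbalance.

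**Conclusion.** The point holds as a matter of efficiency and of a badly specified secondary model. A reader might infer that the primary test is invalid or produces excess false positives. It does not: null rejection stays at or below about 5%.

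The primary test forgoes a gain of about −0.4 points (enrolment status not prognostic), +0.7 to +0.9 (OR 2), +1.5 (OR 3) or nearly +4 (OR 5). This assumes 30% positivity, complete status and the site odds ratios in the table; neither the positivity nor the associations are in the documents.

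The regression needs correction whatever the power gain. Its trigger is undefined, number of study visits is post-randomisation, and malaria treatment received is so on its natural reading. If it is used for an adjusted effect, the computed bias from treatment is 0.3 to 2.2 points on −15.0 for k = 2 to 8, under assumed treatment rates and an assumed unmeasured exposure. No bias was computed for number of visits.

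The change should be made because it is cheap, not because the trial's primary conclusion is unsafe without it.

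**What to change.** Before unblinding:

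1. **Primary Aim 1 test.** Use a CMH test stratified by site and enrolment *P. falciparum* status, with a Mantel-Haenszel risk difference and 95% CI. Define status by smear or PCR on the enrolment sample taken before the first dose. Keep missing status as its own category so that no woman is excluded. If a blinded review finds enrolment PCR largely incomplete, stratify by site alone.
2. **Sensitivity analysis.** Keep the crude chi-square and state whether it is continuity-corrected, since 134 per arm implies the correction and 121 does not.
3. **Supportive model.** Replace the imbalance trigger with one prespecified model using named covariates fixed before the first dose. Remove number of study visits and malaria treatment received after enrolment. Use CD4 count, ART adherence and bed net usage only where an enrolment value exists.

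**Cost.** Analysis-plan wording, a few lines of SAS and no new samples. Enrolment PCR must be complete before analysis, and sample times must be checked against first-dose times. Section XIV.b may make later testing of dried blood spots optional in the consent (the text is ambiguous), so some results may be missing. If enrolment status is not prognostic, about 0.4 power points are lost, or up to about 0.7 with missing status.
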